## **Part II –Interventional Period**

### **Visit 4b**

1st Stimulation Visit – (Approx Time: 1 hour)

There will be 10 stimulation visits to be completed over the next 2 consecutive weeks (ideally Monday to Friday of each week). The subject will receive either 20 minutes of active tDCS in conjunction with active TUS, or sham tDCS in conjunction with sham TUS per day for the course of their stimulation visits.

#### *Randomization:*

Once eligibility and consent have been approved and completed, after all baseline evaluations and immediately before the first stimulation session of Part II, stratified blocked randomization will occur using the randomized list generated by an automatic web-based randomization program ([www.randomization.com](http://www.randomization.com)). Randomization will be based on placebo effect above or below -17.3% according to preliminary data. A staff member who is not involved in any of the study procedures will be responsible for creating the randomization list and monitoring it during the study. Subjects will be randomly assigned to treatment or placebo groups in a 1:1 allocation ratio. We will use permuted blocks of variable sizes (4) in a random manner to minimize the risk of study staff guessing at the next allocation. Randomization order will be kept in sealed envelopes.

#### *Blinding:*

All subjects and investigators will be blinded to the group assignment except for the co-investigators providing stimulation and staff involved in the randomization process (the latter would otherwise not be involved in study procedures). Only the staff involved in the randomization will be authorized to break the blind if there is a clinical need as requested by the PI, clinical care providers, Medical Monitor, or IMC. The patients will remain blinded until they have completed all visits (whether they complete all 23 visits or drop out early), or in the case of an adverse event necessitating un-blinding.

If the subject receives sham stimulation during Part II, he/she may re-enroll into an open label portion of the study, where he/she will receive 10 days of active tDCS/TUS. Un-blinded co-investigators (e.g., who provided stimulation) will coordinate with subjects electing to enter into the open label phase, which will be conducted by the un-blinded study staff. In the open label phase, we will complete the VAS assessments on Day 5 and Day 10 of stimulation. This

collected data will not be analyzed with the main data collected in the study. This data will be used for exploratory analyses only.

After stimulation subjects will complete the following assessments:

- Visual Analog Mood Scale (VAMS)
- Mini Mental State Examination (MMSE)
- Stroop test
- Neurological and Physical Exam
- EEG recording \*
- Adverse Events (AE)
- Visual Analogue Scale (VAS) for Pain

\* *The EEG can be performed at anytime during the first week of stim (V4b-V8).*

### Visits 5-7

2-4th Stimulation visits – (Approx Time: ¾ hour)

During the next 3 stimulation sessions – the subject will receive either 20 minutes of active tDCS in conjunction with active TUS, or sham tDCS in conjunction with sham TUS.

Before stimulation, the subject will complete a series of assessments:

- Visual Analogue Scale (VAS) for Pain
- Pain/Medication Diary

After stimulation subjects will complete the following assessments:

- Visual Analog Scale (VAS) for Pain
- Visual Analog Mood Scale (VAMS)
- Mini Mental State Examination (MMSE)
- Stroop Test
- Adverse Events Questionnaire (AEs)
- MRI at Martinos Center\*\*\*

\*\*\* *The MRI will be taken at most one time for each subject that is eligible for Part II at any time during the remaining of the study, even after the last follow up visit.*

### Visit 8

5th Day of stimulation – (Approx Time: 1 ¾ hours)

Before stimulation, the subject will complete a series of assessments:

- Visual Analogue Scale (VAS) for Pain
- Pain/Medication Diary

After stimulation subjects will complete the following assessments:

- Visual Analog Mood Scale (VAMS)
- Mini Mental State Examination (MMSE)
- Stroop test
- Neurological and Physical Exam

- EEG recording\*\*
- Adverse Events (AE)
- Visual Analogue Scale (VAS) for Pain
- Quantitative Sensory Testing (QST)
- NIH CLBP RMD instrument
- 29-PROMIS short form
- Beck Depression Inventory (BDI)

### **Visit 9**

6th Day of Stimulation – (Approx Time: ¾ hour)

Before stimulation, the subject will complete a series of assessments:

- Urine pregnancy exam (if applicable)
- Visual Analogue Scale (VAS) for Pain
- Pain/Medication Diary

After stimulation subjects will complete the following assessments:

- Visual Analog Scale (VAS) for Pain
- Visual Analog Mood Scale (VAMS)
- Mini Mental State Examination (MMSE)
- Stroop test
- Adverse Events Questionnaire (AEs)

### **Visits 10-12**

7-9th Day of Stimulation visits – (Approx Time: ¾ hour)

Before stimulation, the subject will complete a series of assessments:

- Visual Analogue Scale (VAS) for Pain
- Pain/Medication Diary

After stimulation subjects will complete the following assessments:

- Visual Analog Scale (VAS) for Pain
- Visual Analog Mood Scale (VAMS)
- Mini Mental State Examination (MMSE)
- Stroop test
- Adverse Events Questionnaire (AEs)

### **Visit 13**

10th Day of stimulation – (Approx Time: 2 hours)

Before stimulation, the subject will complete a series of assessments:

- Visual Analogue Scale (VAS) for Pain
- Pain/Medication Diary

After stimulation subjects will complete the following assessments:

- Visual Analog Mood Scale (VAMS)
- Mini Mental State Examination (MMSE)
- Stroop test
- Neurological and Physical Exam
- Adverse Events (AE)
- Visual Analogue Scale (VAS) for Pain
- Quantitative Sensory Testing (QST)
- NIH CLBP RMD instrument
- 29-PROMIS short form
- Beck Depression Inventory (BDI)
- Walking Test
- Postural Stability/Standing Test
- One Leg Stance Test
- Trunk Mobility Test

### **Visit 14, 15, 16, 17 and 18**

Bi-weekly stimulation visits— (Approx Time:  $\frac{3}{4}$  hour)

Before stimulation, the subject will complete a series of assessments:

- Visual Analogue Scale (VAS) for Pain
- Pain/Medication Diary

After stimulation subjects will complete the following assessments:

- Visual Analog Scale (VAS) for Pain
- Adverse Events Questionnaire (AEs)

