### **III. STUDY PROCEDURES**

Because our protocol involves a run-in phase (Part I), we expect that up to 90 patients may enter the run-in phase so we will be able to randomize 40 eligible subjects to participate in this study (in phase II). When the target number of 40 subjects (for phase II) entering the randomized phase

(Part II) is completed, enrollment will end. Subjects who passed the run-in phase (Part I) successfully will then be randomly assigned to receive treatment in Part II with active tDCS+active TUS (n=20) or sham tDCS+sham TUS (n=20 inactive transducers).

**General Study Outline:** This two-Part study will consist of 23 visits over the course of about 15 weeks. After Visit 1, the remaining Part I of the study will take about a week (Visits 2-4a). Prior to any assessments, the subject will consent to participate in both Part I and Part II, pending that the subject fits the additional eligibility criteria\* of the run-in period. After completion of Part I, eligible subjects will continue onto Part II, the main interventional portion of the trial. Part II of the study will take place over the remaining weeks (Visits 4b-23).

*Part I Study Flow – Run-in Period (Visits 1-4a):*

- Screening Visit
- Run-in Visit 2&3 – sham stimulation visits
- Rescreening Visit

*Part II Study Flow – (Visits 4b-23):*

- 10 sessions of tDCS stimulation over 2 weeks
- Bi-weekly sessions of tDCS stimulation over 3 weeks
- 4 Follow-Up Visits – 2 week, 4 weeks, 6 weeks, and 8 weeks post-stimulation

Eligibility criteria for Part II include:

- VAS pain score greater than 1 following either of the two SHAM stimulation sessions [97] during Part I and pain reduction not greater than 72.52% (i.e. not a large placebo response)
- Stable pain intensities (defined as a difference in pain intensities less than or equal to 4 (on a 0-10 VAS scale) between the average over the week prior to visit 2 and the average over the week prior to visit 4a [96])
- High adherence during the Run-in stimulation visits (defined as completing both Run-in stimulation visits within approximately one week)
- VAS pain weighted average  $\geq 3$  prior to randomization during visit 4a (i.e. not exhibiting low baseline pain)

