#### Screening Procedures:

At Screening, the PI and/or a co-investigator will once more conduct a review of inclusion/exclusion criteria to determine the subject's eligibility for enrollment. Study procedures will be reviewed with the subject, and documentation of informed consent will be obtained.

At Screening the following procedures will be completed:

- Discuss study-specific procedures with the subject.
- Review inclusion and exclusion criteria.
- Obtain a signed and dated consent form.
- Conduct a Demographics Survey and the Beck Depression Inventory.
- Urine pregnancy exam (if applicable).

This visit can be done remotely (There will be an electronically signed consent form, using Mass General Brigham REDCap eConsent and the visit will be done either by telephone or Zoom Healthcare)

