### **Visit 19**

Last bi-weekly stimulation visit— (Approx Time: 2 hours)

Before stimulation, the subject will complete a series of assessments:

- Visual Analogue Scale (VAS) for Pain
- Pain/Medication Diary

After stimulation subjects will complete the following assessments:

- Visual Analog Mood Scale (VAMS)
- Mini Mental State Examination (MMSE)
- Stroop test
- Neurological and Physical Exam
- EEG recording
- Adverse Events (AE)
- Visual Analogue Scale (VAS) for Pain
- Quantitative Sensory Testing (QST)
- NIH CLBP RMD instrument

- 29-PROMIS short form
- Beck Depression Inventory (BDI)
- Walking Test
- Postural Stability/Standing Test
- One Leg Stance Test
- Trunk Mobility Test

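### No pregnancy test is listed at the six twice-weekly stimulation sessions, although testing is about weekly up to Visit 9; two added tests would be a cheap safety improvement.

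*Combined protocol and SAP*

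**What the plan says.** Section II (Subject Selection) makes pregnancy exclusion 1. The test is listed at screening (Visit 1), before the first run-in sham session (Visit 2), at rescreening (Visit 4a) and before the sixth Part II session, where the Visit 9 list opens with "Urine pregnancy exam (if applicable". An eligible subject completes Visit 4b, the first Part II stimulation, on the same day as Visit 4a.

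The Part II study flow in section III gives ten sessions over two weeks and then a three-week phase. That later phase covers Visits 14-18, headed "Bi-weekly stimulation visits", and Visit 19, headed "Last bi-weekly stimulation visit". Before stimulation, both sections list the VAS for pain and the pain/medication diary. Neither lists a pregnancy test before or after stimulation, although both include adverse-event questions.

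For sham subjects, the Blinding section says that a subject "he/she may re-enroll into an open label portion of the study, where he/she will receive 10 days of active tDCS/TUS". It adds: "In the open label phase, we will complete the VAS assessments on Day 5 and Day 10 of stimulation". It names no other open-label assessment.

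**The concern.** Visit 9 shows that the plan checks for pregnancy after randomisation as well as at entry. Up to that visit, each week of stimulation begins with a test on the ideal schedule, including the run-in week, when only sham is given. The test then drops off the lists while stimulation goes on for three more weeks, and the text gives no reason.

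The stake is patient safety only. If the lists are followed as written, a pregnancy that begins or first becomes detectable after Visit 9 has no listed test to find it before the six twice-weekly sessions, which are active for half of the randomised subjects. The open-ended adverse-event questions could bring out a pregnancy that the subject knows about, but not one that she does not.

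**Working it through.** The plan gives no figure to reproduce. The check is a count of the test entries plus calendar arithmetic.

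**Inputs.** Tests at Visits 1, 2, 4a and 9 (visit lists). Visit 4a on the same day as Visit 4b (Visit 4a section). Ten daily sessions over two consecutive weeks, ideally Monday to Friday (Visit 4b section). Six further sessions, Visits 14-19, over three weeks (section III), so 6 / 3 = 2 per week.

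**Assumed calendar.** Day 1 is a Monday and is Visits 4a and 4b. Daily sessions fall on days 1-5 and 8-12, which puts Visit 9 on day 8. The twice-weekly phase fills weeks 3-5.

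**Spacing of tests up to Visit 9.** Visit 4a is about a week after the first baseline measurements at Visit 2, and Visit 9 is 8 - 1 = 7 days after Visit 4a.

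**Daily course.** Days since the last listed test are 0, 1, 2, 3, 4 and again 0, 1, 2, 3, 4. With a Wednesday start and weekends off, sessions 1-5 fall 0, 1, 2, 5 and 6 days after the Visit 4a test.

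**Twice-weekly phase as listed, and with tests added at Visits 14 and 17.** Days since the last listed test = session day - 8. Days with the added tests = session day - day of the most recent test.

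| Visit | Mon/Thu day | Days since Visit 9 | Tue/Fri day | Days since Visit 9 | Days since test, with tests at Visits 14 and 17 (either pattern) |
|---|---|---|---|---|---|
| 14 | 15 | 7 | 16 | 8 | 0 |
| 15 | 18 | 10 | 19 | 11 | 3 |
| 16 | 22 | 14 | 23 | 15 | 7 |
| 17 | 25 | 17 | 26 | 18 | 0 |
| 18 | 29 | 21 | 30 | 22 | 4 |
| 19 | 32 | 24 | 33 | 25 | 7 |

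The interval as listed is therefore 7 to 25 days across the two patterns. With the added tests the maximum is 7 days.

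**How many events this could concern.** The documents give neither the number of applicable women (ages run from 18 to 85) nor a pregnancy rate. Suppose that 10-30% of the 20 active-arm subjects are applicable, which is 2 to 6 women, and that the chance of pregnancy is 0.5-3% per woman per month. Over about 25 days (0.82 month), the expected number is 2 x 0.005 x 0.82 = 0.008 at the low end and 6 x 0.03 x 0.82 = 0.15 at the high end. Both ranges are assumptions.

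**The case against.** The best answer is that nothing stated is violated. Pregnancy is an entry exclusion, listed apart from the contraindications to stimulation. The plan nowhere commits to retesting up to the last session, and how often to retest is a choice among reasonable options. All of that stands, and it is why the point is only an improvement to consider.

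Three stronger readings are tempting, and the documents do not support them.

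- *No other safeguard exists.* A reader might infer this from the visit lists. But consent pages are not part of the text reviewed, and the Blinding section refers to a Medical Monitor and an IMC whose duties are not described in it. Contraception, reporting or stopping terms may exist there. They would not put a test on the Visit 14-19 lists, but their absence cannot be asserted.
- *Sham subjects start open-label active stimulation untested, long after Visit 9.* The open-label text is a short paragraph under Blinding, not a visit schedule, so its silence is weak evidence. It speaks of re-enrolment, and the Visit 1 screening, which includes the pregnancy test, has staff "conduct a review of inclusion/exclusion criteria to determine the subject's eligibility for enrollment". Repeating that screening is a natural reading, and on it no long interval arises.
- *Many sessions are at risk.* Multiplying six sessions by the assumed 2 to 6 women gives 12 to 36 active sessions. That counts sessions given to women who could become pregnant, not to women who are, and it rests on an assumed share. The expected number of pregnancies is well below one.

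The contrast with the daily course also depends on the calendar. A midweek start widens the daily intervals to 6 days, so the contrast is less sharp, but it remains.

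**Conclusion.** The point holds as a low-cost safety improvement to consider. The plan tests about weekly from Visit 2 to Visit 9 and lists no test at the remaining six twice-weekly sessions, which fall about 7 to 25 days after the last one. Those day counts assume the ideal Monday start and two sessions in each of weeks 3-5, and real scheduling would shift them. The likely number of undetected pregnancies in a trial of this size is very small, and no fetal hazard is stated. Sample size, power, alpha and analysis are untouched. For the open-label portion, the documents support only a request for clarification.

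**What to change.** Add the existing test line, if applicable, to the pre-stimulation list at Visit 14 and once more in the twice-weekly phase, for example at Visit 17. Apply it in both arms so that testing does not hint at allocation. State that further stimulation is withheld if a test is positive. In the open-label paragraph, confirm that re-enrolment repeats the Visit 1 screening, including the pregnancy test, before the first active session.

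The cost is two kits and a few minutes per applicable randomised subject. If 10-30% of the 40 are applicable (an assumption), that is 4 to 12 subjects and 2 x 4 = 8 to 2 x 12 = 24 kits. The test is already in use, so no new type of procedure or staff is needed. The stopping rule does add some work: the protocol should say how a discontinuation, and any unblinding it prompts, will be handled.

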### **Visit 19**

Last bi-weekly stimulation visit— (Approx Time: 2 hours)

Before stimulation, the subject will complete a series of assessments:

- Visual Analogue Scale (VAS) for Pain
- Pain/Medication Diary

After stimulation subjects will complete the following assessments:

- Visual Analog Mood Scale (VAMS)
- Mini Mental State Examination (MMSE)
- Stroop test
- Neurological and Physical Exam
- EEG recording
- Adverse Events (AE)
- Visual Analogue Scale (VAS) for Pain
- Quantitative Sensory Testing (QST)
- NIH CLBP RMD instrument

- 29-PROMIS short form
- Beck Depression Inventory (BDI)
- Walking Test
- Postural Stability/Standing Test
- One Leg Stance Test
- Trunk Mobility Test

### **Visit 20, 21, 22, and 23**

Follow-Up Visit – Approximately 2 week, 4 weeks, 6 weeks, and 8 weeks post-stimulation –  
(Approx Time: 1 ¾ hours)

- Visual Analog Mood Scale (VAMS)
- Mini Mental State Examination (MMSE)
- Stroop test
- Neurological and Physical Exam
- Adverse Events (AE)
- Visual Analogue Scale (VAS) for Pain
- Pain/Medication Diary
- Quantitative Sensory Testing (QST)
- NIH CLBP RMD instrument
- 29-PROMIS short form
- Beck Depression Inventory (BDI)
- Walking Test
- Postural Stability/Standing Test
- One Leg Stance Test
- Trunk Mobility Test

## **DESCRIPTION OF ASSESSMENTS:**

A rater blind to the treatment arm will administer the following tests (also used in our previous study [102]):

*Visual Analogue Scale (VAS) for Pain:* The VAS is a common assessment used which asks subjects to self-reportedly measure their pain on a visual scale (i.e., unbearable to none). This will help us to monitor changes in subjects' pain levels when they come in for sessions.

*Pain/Medication Diary:* To help monitor pain levels, as well as safety, subjects will keep a diary listing their daily medications and pain levels when not at the laboratory.

*Quantitative Sensory Testing (QST) for Pain:* The QST is a common assessment used which measures the detection threshold of accurately calibrated sensory stimuli. It consists of assessing: Mechanical Pain Threshold (MPT), Mechanical Temporal Summation (TS), and Pressure Pain Thresholds (PPT). The QST is founded on:

- *Von Frey Assessment:* This test does not pose a risk to subjects and will help us to monitor whether there are changes in subject's ability to perceive nociceptive stimuli.
- Mechanical temporal summation (TS): “TS is assessed by having the participant rate their pain after a single stimulus is applied for ~0.5 s and then again after a series of 10 stimuli are applied at ~1-s intervals. Temporal summation is

calculated as the difference between the rating of the series of 10 stimuli and the rating of the single stimulus.”[103] A 6.65, 300 g Von Frey filament will be used as the stimulus unless the subject does not feel comfortable performing the test with the heaviest fiber. If so, we will reduce the weight of the fiber until it is tolerable by the subject or we will perform the test with the fiber the subject rated as painful, as long as it is tolerable, during the Von Frey Assessment.

- *Pain-Pressure Tests (PPT)*: PPT will be determined using an FDA approved algometer as described in the research strategy. This assessment is often used as a measurement for pain-pressure thresholds in pain patients. Thus, it poses no significant risk to subject safety. The FDA approved algometer will be alternately applied three times, in counter-balanced fashion, ipsilateral to the most painful low back area (if bilateral pain, performed contralateral to the dominant side) to determine participants’ baseline pressure pain thresholds (PPTs). Participants will indicate when the increasing pressure stimulation first became painful (via PPT).
- *Conditional Pain Modulation (CPM)*: Following the baseline PPT determination, participants will undergo a series of cold water immersions that will consist of placing the contralateral hand, up to the wrist, into cold water for about 1 minute. The cold water will be maintained at a temperature that produced a moderately painful sensation as during initial health assessment. Participants will be told they can remove their hand from the water at any time. Approximately 30 seconds after initiation of each cold water immersion, while the hand is still immersed, the algometer will be used to deliver noxious mechanical stimulation to either the palm or the back. Participants will indicate when the increasing pressure stimulation first becomes painful, which represented their conditioned PPTs. There will be a 2-minute rest period between each CPM trial [60].

*EEG recording*: EEG recordings will be taken at the first baseline visit before the first sham stimulation session, one time at any point during the first week of stimulation of Part II and one in the last stimulation visit, to monitor brain activity and saved for post recording evaluation.

*MRI*: Patient MRIs will be assessed to correlate brain anatomy with patient pain characteristics and response to treatment.

*Neurological and Physical Exam*: Trained study staff will conduct baseline and follow-up neurological examinations focused to ensure subject safety one week prior to stimulation, on the first day of stimulation, at the end of each stimulation week, and during each follow up visit [104].

*Visual Analog Mood Scale (VAMS)*: This is a self-assessment scale in which subjects rate their own emotions, including anxiety, depression, stress, and sleepiness along a 100 mm line.

*Mini Mental Status Exam (MMSE)*: This is a sensitive, valid and reliable 30-point questionnaire that is used extensively in clinical and research settings to measure cognitive impairment. This instrument will be used as a brief screening of cognitive abilities. The MMSE will be administered at the baseline evaluation and every subsequent visit.

*Stroop test: 4-Choice Reaction Time:* Patients will be seated in front of a computer screen placed at eye level. Subject will we ask to identify the colors of each word that will appear on the screen. The Stroop test will be administered at the baseline evaluation and every subsequent visit.

*Adverse Effects Questionnaire:* At each session after stimulation begins, subjects will complete a questionnaire to evaluate potential adverse effects of stimulation (headache, neck pain, mood alterations, and seizures) on a 5-point scale. The scale will also be administered at the follow-up. The subjects will be asked whether they have experienced any side effects in an open-ended manner and they will then be specifically asked about headache, neck pain, scalp pain, scalp burns, tingling, skin redness, sleepiness, trouble concentrating, and acute mood change. If any side effects are reported, the degree of relatedness to the intervention will be assessed.

[figure not shown]
We will be investigating adverse effects using open-ended questions. An AE can be any unfavorable and unintended sign, symptom, or disease temporally associated with the use of a treatment, whether or not considered related to the product.

Examples of AEs are as follows:

- Subjective symptoms offered by or elicited from the subject
- Objective signs observed by the Investigator or other study personnel

All concurrent diseases that occur after the start of the study, including any change in severity or frequency of preexisting disease will be investigated in several domains including: seriousness, severity, length of duration, and if any causal relationship exists with the intervention [53].

*Walking Test:* Patients will be asked to walk at comfortable speed for 10 meters to assess gait patterns. Quantitative objective metrics of walking will be extracted from the recorded data such as walking speed, gait asymmetry, stride length, and walking smoothness [105-108].

*NIH CLBP RMD and PROMIS 29 instruments- Patients will fill out questionnaires are designed to assess the low back pain and the impact of pain on function, psychological, sleep, and related activities.* The NIH CLBP Research Task Force (RTF) Recommended Minimum Dataset (RMD) instrument is made of the components of the Patient Reported Outcomes Measurement Information System (PROMIS) instrument [116], the Subgroups for Targeted Treatment (STarT) Back instruments[117], and the RTF Impact classification (see NIH Research Task Force (RTF) for low back pain assessment recommendations [5]). Components of the 29-PROMIS short-form [116] not included as part of the NIH Minimum Data Set Instrument (e.g., elements of anxiety and fatigue) will also be assessed.

*Beck Depression Inventory (BDI)* is used for assessing the severity of depression [95].

If a subject is not comfortable to perform one of the described assessments or subject schedule doesn't allow, any assessment not performed other than VAS pain, will be noted in the study binder and proceed with the visit.

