#### **IV. BIOSTATISTICAL ANALYSIS**

Data forms and questionnaires will be coded in a standardized manner, and double-entered into our database. Digital measures/recordings will be similarly tracked in our database and regularly backed up. Analyses will be conducted using standard statistical software such as SAS and Matlab.

Sample size calculations and data analysis:

*Aim 1:*

For planning sample size calculation for this study, we considered the surrogate pain outcomes as the main outcome for such analysis; considering the two studies showing significant alterations of these outcomes in NSCLBP [118], an effect in the active tDCS in conjunction with active TUS that is twice of the effect in SHAM tDCS in conjunction with SHAM TUS would be adequate. Considering this effect size and a power of 80% and alpha of 5%, we would need 6 subjects per group for a total of 12 subjects. Therefore considering dropouts and also to increase the sample in phase I for the clinical outcome, we increased the sample to 20 subjects (10 for each arm), that would also give a power to detect significant differences of 2 points in VAS between the 2 groups; though the clinical outcome is not the main outcome in phase 1. For Phase 2, we doubled the sample size as to have enough power to detect a difference of 1.3 in VAS between the two groups that would therefore be adequate to demonstrate a clinically meaningful difference between the two groups. We considered differences smaller than that not clinically meaningful.

All analyses will be conducted according to the principle of intention-to-treat (using regression-based single imputation method). We will also perform an additional sensitivity analysis in

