which we will use the method of last observation carried forward. The primary outcome will be TS and CPM [118] (in phase 1) and VAS (in phase 2) changes as indexed by VAS scores, biomechanical function changes as indexed with the motion analysis suite, and global self-assessment changes. Differences between the two groups (active tDCS in conjunction with active TUS and SHAM tDCS in conjunction with SHAM TUS) will be tested using Student's t-test and, in addition, we will adjust for important baseline variables and also test the time effect in general mixed longitudinal models. This model will be used for the primary and secondary outcomes. Secondary analyses will be conducted in an exploratory manner (no correction for multiple comparisons). Similar analysis will be conducted for the adverse effects measuring continuous outcome and for the categorical outcomes we will use Fisher's exact test. In both cases, for safety analysis we will use uncorrected p-value to increase the likelihood of detecting detrimental adverse effects.

332-6.

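### Motion tests skipped because of pain are not distinguished from schedule gaps and are imputed from patients who performed them, so the arm difference can be biased, in a direction that depends on who skips.

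*Combined protocol and SAP*

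**What the plan says.** The skip rule closes the section on description of assessments. It gives two reasons for omitting a test: "If a subject is not comfortable to perform one of the described assessments or subject schedule doesn't allow". Both lead to the same step: "any assessment not performed other than VAS pain, will be noted in the study binder and proceed with the visit". The wording requires that the omission be noted. It does not require the reason to be recorded or coded.

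Under IV. Biostatistical Analysis, missing values are handled in one sentence: "All analyses will be conducted according to the principle of intention-to-treat (using regression-based single imputation method"). Predictors, the role of treatment arm and any residual draw are not specified. The only other treatment of missing data is a sensitivity analysis in "which we will use the method of last observation carried forward".

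The outcome sentence in that section begins "The primary outcome will be TS and CPM [118] (in phase 1) and VAS (in phase 2) changes as indexed by VAS scores" and continues with "biomechanical function changes as indexed with the motion analysis suite, and global self-assessment changes". The motion tests (walking, standing, one-leg stance, trunk mobility) are scheduled at Visit 4a as baseline, at Visits 13 and 19, and at follow-up Visits 20 to 23. VAS pain is scheduled at each of these visits and is exempt from the skip rule.

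**The concern.** In low back pain, declining a trunk or stance test because it hurts may itself be a poor result on that test. A regression fitted to patients who performed the test predicts what a performer with the same covariates would have scored. If non-performers would have done worse, the imputed value is too good. LOCF does not address this, since it carries forward a value from a visit at which the patient could still perform.

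Nothing in the plan lets a skipped value be worse than predicted. Because the reason need not be recorded, the analyst could not later separate pain from scheduling. The motion outcomes stand in the same sentence as the phase 2 primary outcome, so a biased arm difference there would affect how the trial is read.

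**Working it through.** **The plan's own figure.** The plan states no sample size, power or skip rate for the motion outcomes. Its phase 2 statement is 20 per arm to detect 1.3 VAS points, with no SD. A two-sided 5% t-test with 20 per arm has 80% power at 0.909 SD, so 1.3 points would imply an SD of 1.3 / 0.909 = 1.43. That figure can be neither confirmed nor faulted. It only shows that an effect of about 0.9 SD is what a trial of this size can detect, and 0.9 SD is therefore the assumed true effect below.

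**Simulation 1: poor performers skip in both arms.** Assumptions, none from the documents: baseline–outcome correlation 0.6; patients scoring below a threshold skip with probability 0.8; stochastic regression imputation; t-test on change; 3,000 trials per scenario. With the sham mean at 0 and the active mean at 0.9, the skip rates are:

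- Threshold −1.0: sham 0.8 × Φ(−1.0) = 12.7%; active 0.8 × Φ(−1.9) = 2.3%.
- Threshold −0.5: sham 0.8 × Φ(−0.5) = 24.7%; active 0.8 × Φ(−1.4) = 6.5%.

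Power with complete data: the SD of change is √(2 × (1 − 0.6)) = 0.894, the standardised effect is 0.9 / 0.894 = 1.01, and power is 87%.

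| Missing, sham / active | Imputation model | Estimate (true 0.90) | Power |
|---|---|---|---|
| 13% / 2% | baseline only | 0.72–0.73 | 69% |
| 13% / 2% | baseline + arm | 0.79 | 77% |
| 13% / 2% | baseline + arm + concurrent VAS | 0.80 | – |
| 25% / 6% | baseline only | – | 52–53% |
| 25% / 6% | baseline + arm | – | 70% |
| 25% / 6% | baseline + arm + concurrent VAS | 0.75 | – |

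The VAS rows assume a VAS–outcome correlation of about 0.5. LOCF gave 0.82 and 0.78 SD in the two scenarios, so it is biased too. A true harm is also pulled toward zero: −0.5 SD came out at −0.39 SD with arm in the model.

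**Simulation 2: other skip patterns.** This used different assumptions: deterministic imputation, correlation 0.5, soreness–outcome correlation 0.6, and 10% or 20% of all tests skipped.

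- Poorest performers in either arm: 0.68 / 0.76 / 0.80 SD at 10% skipped and 0.53 / 0.68 / 0.74 SD at 20% (baseline only / + arm / + arm + VAS). The largest loss is (0.90 − 0.53) / 0.90 = 41%.
- Skipping driven only by concurrent soreness, with arm and VAS in the model: 0.89–0.90 SD, so no material bias.
- Only active-arm patients skip: 0.98 to 1.33 SD, an enlargement of 9% to 48%.
- No true effect, arms skipping alike: estimate about 0.

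**Effect of leaving arm out.** With skipping random at 13% and 2%, a baseline-only model still gave 0.83 SD. Part of the fall to 0.72 therefore comes from omitting arm, not from pain-related skipping.

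**Type I error.** With arm in a single-imputation model, Simulation 2 gave a two-sided error of 6.5–7.4% at 10% skipped and 8–10.5% at 20%, because imputed values are analysed as if observed.

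**The case against.** A reader might infer that imputation necessarily shrinks the arm difference. The documents do not support that. They predict no imbalance in skipping, and the bias can be zero, toward zero or away from zero depending on who skips.

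A reader might also infer that no missing-at-random method could help. That is too strong. VAS pain may not be skipped, so if soreness drives skipping, a model with arm and concurrent VAS removes nearly all the bias. If skipping depends on performance itself, the model removes only part, and 0.80 SD remains against 0.90. The plan names no predictors, so neither outcome is assured.

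A third inference is that soreness caused by stimulation would be hidden. It would not be: the adverse-effects questionnaire and VAS both record discomfort.

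The sensory tests are less exposed. For temporal summation (TS), when the heaviest filament is not tolerated, "If so, we will reduce the weight of the fiber until it is tolerable by the subject". The pressure pain threshold (PPT) normally registers tenderness as a low value. TS and conditioned pain modulation are primary only in phase 1.

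Finally, worst-rank scoring looks best where the simulated skippers are the worst performers, which is nearly true by construction: power there was 85–87%. When skipping followed soreness, it had 79–82% power against 85–86% for imputation with arm and VAS. It therefore belongs among the sensitivity analyses and should not replace the main one.

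What stands is the undifferentiated skip note, the unspecified imputation model, and the absence of any analysis for informative skipping.

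**Conclusion.** The concern holds for the motion outcomes, as a risk whose direction is not known in advance. If poor performers skip by the same rule in both arms and stimulation has a true effect, the difference is pulled toward zero. If skipping is concentrated in the active arm, it is enlarged. If there is no true effect and the arms skip alike, the estimate is unbiased.

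Under an assumed 13% sham and 2% active missing, 0.90 SD becomes about 0.72–0.80 SD depending on the predictors. These sizes rest wholly on assumed skip rates, correlations and skip rules, and a low skip rate would make the matter minor. The phase 2 VAS outcome is not affected by the skip rule.

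The change is worth making because a reason not recorded at the visit cannot be reliably recovered later.

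**What to change.** 1. **Visit form.** For each omitted test, record a coded reason: unable or unwilling because of pain; other discomfort; schedule. Report pain-related non-performance by arm and visit. Patients remain as free to decline as before.
2. **Imputation model (IV. Biostatistical Analysis).** For the motion outcomes, name the predictors: arm, baseline value and the concurrent VAS pain score. Visits 13 and 19 have VAS before and after stimulation and list the motion tests after it, so state which VAS is used. Adding arm raises the type I error of single imputation, as shown above. When the paragraph is redrafted, say how imputation uncertainty will be reflected in the test.
3. **Sensitivity analysis beside LOCF.** Give pain-related skips the worst rank in the clinically worse direction of each measure (low for walking speed, high for gait asymmetry). Compare arms with a rank test at named visits, for example Visits 13 and 19. Treat schedule gaps as missing at random, and state how a test skipped at the Visit 4a baseline is handled.

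The cost is one form field, a short paragraph in the analysis section and one extra analysis, whose result is rank-based and gives no mean difference.
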